7.5. Retention Plan

Reimbursement. A \$25 electronic gift card will be provided upon completion of baseline, \$25 electronic gift card for their 1-month follow up, \$30 for their 3-month follow up, and \$35 for their 6-month follow up assessment. Participants will only receive compensation upon completion of each phase of the study. The compensation will be sent electronically to the email address provided by the participant at the beginning of the study. The initial baseline session will take approximately 75-90 minutes and each of the follow-up assessments should take approximately 30 minutes to complete. This gradual increase in payment (\$25, \$30, \$35) will help ensure we have strong follow-up rates through the 6-month intervention period and is consistent with payment schedules used in other studies with this population.

7.5.1 Brown COVID adjustment timeline

- March 6th, 2020 – Last in-person RAVEN session
- March 12th, 2020 - Announcement made about intent to close campus
- March 16th – 20th, 2020 - Classes cancelled
- March 17th, 2020 - Amendment for remote procedures approved
- March 26th, 2020 – First remote RAVEN session
- March 22nd, 2020 - All students off campus
- March 22nd – 27th - Spring break
- March 30th, 2020 - All classes moved to remote
- September 18th – campus re-opens with restrictions, all baseline sessions starting Fall 2020 semester were conducted remotely

7.5.2 UH recruitment post-COVID (remote baseline sessions)

- March 5th, 2020 – Last in-person RAVEN session
- March 10th, 2020 – Work remote suggested (not a policy)
- March 11th, 2020 – Classes paused for transition to online, work remotely if possible
- March 17th, 2020 – Social distancing/take-out only dining begins
- March 17th, 2020 - Amendment for remote procedures approved
- March 24th, 2020 – Stay-at-home order official from Harris county
- April 8th, 2020 – First remote RAVEN session
- May 5th, 2020 – Essential (i.e., can't be done remote) research labs can be opened
- June 1st, 2020 – Campus open to faculty/staff on a limited voluntary basis

7.6 Participant communications

7.6.1 Brown participant communication pre-COVID (in-person sessions; see Appendix A)

All participant email communications are sent from the [contact] email address, using IRB-approved templates. Appointment text reminders are sent using an online texting application, and phone call reminders are made using staff work telephones.

7.6.2 Brown participant communication post-COVID (remote sessions; see Appendix B)

Several changes to participant communications were made as a result of the change to remote baseline administration. (a) Consent is obtained verbally using Zoom, supplemented by confirmation in

the form of checking a consent box on an online form of the Consent document, rather than an in-person signature (b) Baseline sessions, some of which include a brief computerized intervention and discussion with a research assistant, will take place via Zoom rather than in-person (c) Intervention materials, including personalized feedback containing no identifying information, that would have been printed and given in person will now be emailed electronically

7.6.3 UH participant communication pre-COVID (in-person sessions; see Appendix A)

All participant email communications are sent from the [contact] email address, using IRB-approved templates. Appointment text reminders are sent using an online texting application, and phone call reminders are made using staff work telephones.

7.6.4 UH participant communication post-COVID (remote sessions; see Appendix B)

Several changes to participant communications were made as a result of the change to remote baseline administration. (a) Consent is obtained verbally using Zoom, supplemented by confirmation in the form of checking a consent box on an online form of the Consent document, rather than an in-person signature (b) Baseline sessions, some of which include a brief computerized intervention and discussion with a research assistant, will take place via Zoom rather than in-person (c) Intervention materials, including personalized feedback containing no identifying information, that would have been printed and given in person will now be emailed electronically. Participant communication still occurs via the [contact] email address and online texting application, but phone call reminders are no longer used.

8. INTERVENTIONS (see Appendix C for intervention scripts)

8.1. Counter Attitudinal Advocacy Condition. In order to prompt participants to express attitudes inconsistent with current behavior, we have pilot-tested and refined instructions to articulate how to engage in moderate drinking via self-generated PBS in order to avoid negative consequences. By design, inclusion criteria will produce a sample that has engaged in heavy episodic drinking (5+/4+ criteria for men/women, respectively) and experienced at least two consequences. The examples included in the prompt will be personalized to each participant, based on his/her responses to the baseline survey; thus, the examples will represent negative consequences actually endorsed by the participant, to optimize the chance that the argument will be experienced as counter-attitudinal. Therefore, articulating ways to avoid consequences using self-generated PBS strategies is likely to result in dissonance, which can be resolved by increasing the use of those strategies and reducing the frequency or quantity of drinking. Reviews confirm that use of PBS is associated with fewer alcohol-related problems (Pearson, 2013; Prince et al., 2013). Therefore, writing about self-generated ways to use PBS during drinking occasions should produce dissonance that can be resolved by using more PBS, and this resolution of attitude-behavior discrepancy is likely to result in fewer alcohol-related consequences.

8.2. Personalized Normative Feedback (PNF) Condition. Participants in the PNF condition will receive gender-identity specific personalized feedback regarding their alcohol use, consistent with previous NIAAA-funded trials using trained facilitator-delivered PNF as a brief intervention conducted by this team (e.g., R01AA014576). The PNF intervention contains both text and graphic information regarding 1) the student's own drinking quantity and frequency of drinking, 2) perceptions of typical drinking by same-sex students on campus (i.e., perceived descriptive norms), and 3) actual drinking rates by same-sex students' on campus (i.e., actual descriptive norms). Normative feedback for male or female identifying students will use data from same-sex students on campus, whereas normative feedback for non-binary or genderqueer students will use data averaged across all students on campus. The actual norms will be referenced to the survey from which norms were generated (date, N, and campus), which took place on both campuses in March 2019.

The RA will present the PNF sheets, populated by the participant's baseline data and will explain their format, where the normative data came from, and engage the participant in interpreting the graphic feedback. The RA will ask if the student has any questions about the information before concluding the session. This brief discussion is designed to be educational and clarifying, and to roughly equate the amount of interpersonal interaction to that in the CAA condition.

8.3. Assessment Only Control Condition. Participants in the assessment only control condition will receive no intervention. The only contact will consist of completing the baseline assessment in lab as well as email and telephone reminders to complete the 1-, 3-, and 6-month follow-up assessments.

9. STUDY ASSESSMENTS AND PROCEDURES

9.1. Baseline Assessment. (See Appendix C)

9.1.1. Descriptive measures

Demographics will include class year, current residence, age, race, ethnicity, international student status, status as a first-generation college student, height, weight, religion, birth sex, gender identity, relationship status, immigration status and involvement in the Greek system.

Other substance use questions will include the NIDA Modified ASSIST, which assesses lifetime and past month use of tobacco products, cannabis, cocaine, prescription stimulants, methamphetamine, inhalants, sedatives or sleeping pills, hallucinogens and street opioids.

9.1.2. Primary and secondary outcomes

Alcohol consumption will be assessed with the Quantity-Frequency-Peak Alcohol Use Index (QFP; Baer, 1993; Marlatt, Baer, & Larimer, 1995), and the Daily Drinking Questionnaire (DDQ; Collins, Parks, & Marlatt, 1985; Kivlahan, Marlatt, Fromme, Coppel, & Williams, 1990). The Quantity-Frequency-Peak Alcohol Use Index is a five-item questionnaire that includes two items characterizing the occasion where respondents drank the most during the previous month (from which we calculate peak BAC), two items addressing typical weekend drinking in the previous month, and one item addressing typical number of drinking days per week in the past month. Typical weekly drinking and typical drinks per occasion will be assessed with the DDQ. Participants fill in the average number of standard drinks they consumed and the time period of consumption for each day of a typical week in the past month. The primary source for assessing drinking outcomes will be the DDQ, and QFP, which we have used in several previous RCTs in this population.

Alcohol-related negative consequences will be assessed with the 48-item Young Adult Alcohol Consequences Questionnaire (YAACQ; (Read, Kahler, Strong, & Colder, 2006). The YAACQ is a self-administered checklist of problems related to drinking that is tailored to college drinkers; responses are dichotomous (yes/no) and refer to past month. The YAACQ is reliable and free of gender bias.

Protective behavioral strategies will be measured with the 15-item Protective Behavioral Strategies Scale (Martens, Pedersen, LaBrie, Ferrier & Cimini, 2007) The PBSS assesses contingent frequency of using each strategy when drinking (1=never, 6=always) and is reliable and valid for use with college drinkers. This will be supplemented with the 4-item “Alternatives to drinking” factor (e.g., “Found other ways besides drinking to reduce stress”) from the Protective Behavioral Strategies Questionnaire (Sugarman & Carey, 2007).

Drinking intentions will be assessed using a modified version the daily drinking questionnaire (DDQ; Collins, Parks, & Marlatt, 1985; Kivlahan, Marlatt, Fromme, Coppel, & Williams, 1990: Modified DDQ Intentions; Young, Rodriguez, & [name], 2013). Participants fill in the average number of standard drinks they intend to consume and the time period of intended consumption for each day of a typical week in the next month.

9.1.3. Hypothesized moderators

Drinker identity will be assessed using the 5-item Alcohol Self-Concept Scale (ASCS). The ASCS was adapted from the Smoker Self-Concept Scale (Shadel & Mermelstein, 1996), and contains statements about the extent to which drinking plays a part in one's life and personality and others' perceptions of alcohol's role in one's life (e.g., Drinking is a part of 'who I am'). The ASCS is anticipated to serve as a moderator of the CAA interventions in tests of AIM 4. Specifically, we hypothesize that those higher in drinker identity will experience more dissonance and behavior change as a result of the CAA activity. In contrast, individual's who identify more strongly with drinking (Drinking is a part of 'who I am') will be less likely to change following PNF.

Preference for consistency will be assessed using the 9-item Preference for Consistency (PFC) scale. The PFC (Cialdini, Trost, & Newsom, 1995) contains statements such as, "I am uncomfortable holding two beliefs that are inconsistent." The PFC is anticipated to serve as a moderator of the CAA intervention in tests of AIM 2. Specifically, we hypothesize that the CAA will be more efficacious for those reporting a greater preference for consistency as they will change their attitudes and behavior in the argued direction more than those who report a lower preference for consistency. Similarly the PNF should be more efficacious for those with stronger preference for consistency because they are less comfortable deviating from the campus norms.

9.1.4. Hypothesized mediators

Attitudes toward moderate consumption and attitudes toward heavy consumption will be assessed with measures modified from previous research (Hagger et al., 2012; Norman, 2011). For moderate consumption, the stem will read, "Keeping my alcohol drinking within what is considered moderate drinking for adults (i.e. at 4 or fewer drinks for men or at 3 or fewer drinks for women) on each individual occasion over the next month would be..." For heavy consumption, the stem will read, "Having five or more drinks (for males)/four or more drinks (for females) in a sitting over the next month would be..." For both measures, there are five semantic differential scales that range from 1 to 5: unenjoyable-enjoyable, bad-good, harmful-beneficial, foolish-wise, and unpleasant-pleasant. To test AIM 3, changes in attitudes toward heavy drinking and attitudes toward moderate drinking are anticipated to serve as a mediator of the CAA (but not PNF) intervention effects.

Cognitive dissonance will be assessed using the Dissonance Thermometer (Devine, Tauer, Barron, Elliot, & Vance, 1999; Elliot & Devine, 1994; Simmons & Brandon, 2007; Simmons et al., 2004; Simmons, et al., 2013). Items include asking participants how uncomfortable, angry at themselves, shameful, uneasy, friendly (reverse scored), disgusted with themselves, embarrassed, bothered, optimistic (reverse scored), annoyed at themselves, disappointed at themselves, happy (reverse scored), energetic (reverse scored), and good (reverse scored) they feel immediately following the CAA activity. The 3-item affective discomfort factor has been found to be susceptible to cognitive dissonance inductions resembling our CAA procedure, with other target behaviors (Devine et al., 1999; Simmons et al., 2013). In Aim 3 we will test dissonance as a mediator of both CAA and PNF interventions.

Perceived descriptive norms will be measured by a modified version of the Drinking Norms Rating Form (DNRF; Baer et al., 1991). The gender-specific version (Lewis & [name], 2004) assesses perceived typical number of drinks consumed per drinking occasion (e.g., "how many drinks on average do you think a typical male/female Brown/UH student consumes on a given occasion?"), and perceived frequency of drinking occasions (e.g., "how often do you think a typical male/female Brown/UH student consumes alcohol?"). The DNRF assesses perceived typical weekly drinking by having participants fill in the average number of standard drinks they think the typical (male/female) Brown/UH student consumes for each day of the week over the previous month. The DNRF has been used in multiple studies of college drinking and has shown good concurrent and prospective validity ([name], Dillard, Lewis, Bergstrom, & Neil, 2006). In Aim 3 we test changes in descriptive norms as mediators of the PNF (but not CAA)

effects.

Perceived Injunctive norms will also be assessed using an adaptation of the DNRF shown to be reliably associated with respondent drinking (Krieger et al., 2016). This drink-based injunctive norms assessment includes (a) “maximum number of drinks a typical male/female Brown/UH student approves of consuming on one occasion?”, (b) “maximum frequency of drinking a typical male/female Brown/UH student would approve of in a week?”, and (c) “what is the maximum number of drinks a typical male/female Brown/UH student would consider acceptable to consume on each day of the week?.” [name] et al. (in preparation) recently demonstrated support for personalized injunctive norms feedback based using this measure (see preliminary studies). Additionally, injunctive norms will be assessed for negative consequences of drinking. Rating scales will be used to assess how unacceptable and acceptable experiencing specific drinking consequences is believed to be (Prince et al., 2015). These consequences include driving after drinking, drinking enough to pass out, blacking out due to drinking, etc. In Aim 3 we test changes in injunctive norms as mediators of the PNF (but not CAA) effects.

9.2. Follow-up Assessments. At 1-, 3-, and 6- months following their baseline assessment, participants receive an email inviting them to complete each follow-up assessment and containing a link to the online survey. All follow-up assessments will be completed using web-assessment, and measures will be identical to those given at baseline. Participants will receive an additional \$25 electronic gift card for their 1-month follow up, \$30 for their 3-month follow up, and \$35 for their 6-month follow up. This gradual increase in payment will help ensure we have strong follow-up rates through the 6-month intervention period. Each follow up assessment should take approximately 30 minutes.

10. STATISTICAL CONSIDERATIONS

10.1. Sample Size. Power analyses focus on estimating a sample size large enough to detect “true” effects, thereby avoiding Type II errors. Sample size estimates were obtained for intervention contrasts. Necessary sample sizes were assessed via sample size and power equations for multi-level models using the Optimal Design software program. Based on previous findings using CAA and PNF approaches, we anticipate intervention effects relative to the neutral control condition to be in the small to medium range but at least comparable to effects which have been reported for personalized normative feedback, which are typically in the .28 range (e.g., Dotson et al., 2015). Based on the proposed sample size of 600, given four assessment points, we anticipate the ability to detect effects of intervention contrasts and moderation effects across the small to medium range. Considering maximum anticipated attrition rates of 15% (N=510) we will have .70, .80, and .90 power to detect effects sizes of $\delta = .24, .27, \text{ and } .32$, respectively.

10.2. Analysis Plan. Aims will be evaluated using generalized linear mixed models, an extension of general linear models allowing for multi-level data with non-normal distributions (e.g. Atkins, Baldwin, Zheng, Gallop, & [name], 2013; Hedeker & Gibbons, 2006). With respect to evaluating main effects of experimental conditions on drinking, each participant will provide up to four assessments (baseline, 1-month, 3-month, and 6-month follow-up data). Hypotheses will be tested using specific contrast vectors, using a general linear hypothesis framework (Fox, 2008).

Hypotheses associated with Aim 1 will be evaluated examining outcomes as a function of two dummy coded variables representing CAA and PNF with control as the reference group. Time X CAA outcomes will provide direct tests of differences in change between CAA and control groups. We will utilize a Bonferroni correction with Šídák adjustment for correlated outcomes to reduce alpha inflation associated with multiple outcomes (i.e., moderation attitudes, heavy drinking attitudes, dissonance, drinks per drinking day, binge frequency, peak BAC, alcohol consequences, and PBS use).

For these analyses, each participant will provide up to 4 repeated measures (i.e., baseline, 1-month, 3- months, 6-months), yielding up to 2400 Level 1 cases (repeated-measures) across 600 Level 2

cases). Assuming outcomes follow a negative binomial distribution with a natural log link, the following model will be the basis for evaluating intervention effects as specified in Aim 1 hypotheses:

$$\text{Level 1: } \log(E[\text{DV}]_{ti}) = \pi_{0i} + \pi_{1i}(\text{Time})_{ti} + \varepsilon_{ti} \quad \varepsilon_{ti} \sim N(0, I\sigma^2_\varepsilon)$$

$$\begin{aligned} \text{Level 2: } \pi_{0i} &= \beta_{00} + \beta_{01}(\text{site})_i + \beta_{02}(\text{CAA})_i + \beta_{03}(\text{PNF})_i + \beta_{10} + r_{00i} \\ \pi_{1i} &= \beta_{10} + \beta_{11}(\text{site})_i + \beta_{12}(\text{CAA})_i + \beta_{13}(\text{PNF})_i + r_{10i} \end{aligned}$$

where t indexes repeated-measures and i indexes participants. Campus represents the differences between Brown and UH, CAA represents the difference between CAA and the Control group, and PNF represents the difference between PNF and the control group. DV_{ti} represents the outcome vector for each individual at each assessment point. Time_{ti} measures weeks since baseline. Hypotheses associated with Aim 2 will test the relative efficacy of CAA vs. PNF using a non-inferiority design. Following the procedures outlined by Schumi & Wittes (2011), we have consulted a recent metaanalysis to obtain an effect size estimate of PNF efficacy (vs. Control) on drinking quantity ($d = .289$, 95% CI [0.117, 0.451]) and consequences ($d = .157$, 95% CI[0.037, 0.278]) (Dotson, Dunn, & Bowers, 2015). Next, we use the lower bound of each confidence interval as the basis for deriving our margin with respect to declaring non-inferiority. Thus $M1 = 0.117$ for quantity and $M1 = .037$ for consequences; these represent the most conservative estimate of the PNF effect. Then we select a smaller margin (M2) that represents the largest acceptable loss of effect when CAA is compared to PNF. Using a conservative estimate of M2 (50% of M1; USFDA, 2016), we establish non-inferiority if we retain at least half of the effect of PNF. Thus, if the lower bound confidence interval for the effect of CAA vs PNF is larger than half the lower bound estimate of the effects on drinking quantity (.117/2 = .0585) and consequences (.037/2 = .0185), we will be able to declare CAA is non-inferior to PNF.

Hypotheses associated with Aim 3 will evaluate mediators of intervention effects. We will follow procedures described by MacKinnon and colleagues (e.g., MacKinnon, Fairchild, & Fritz, 2007) to assess mediation. Mediation will test indirect effects using the AB products method with bootstrapped standard errors where A will represent effects of intervention contrasts by time interactions on mediators. B will represent the associations of mediators on subsequent drinking outcomes. Both A and B paths will control for baseline outcomes. Hypotheses associated with Aim 4 will follow a similar approach but will add prospective moderators and products of prospective moderators and contrasts

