4. AIMS AND ENDPOINTS

Aim 1. Examine the effects of CAA on alcohol outcomes. Our primary hypothesis is that, relative to AO control, the CAA intervention will (a) increase positive moderate drinking attitudes, (b) decrease positive heavy drinking attitudes, (c) increase attitude-behavior dissonance, and (d) decrease drinks per drinking day, binge frequency, peak BAC, and alcohol consequences, and increase the use of PBS.

Aim 2. Compare the effects of CAA vs. PNF. A secondary hypothesis is that CAA will be no less efficacious than (i.e., not inferior to) PNF in reducing alcohol outcomes as measured by alcohol consumption and alcohol related consequences.

Aim 3. Test specific theory-based mediational pathways. Aim 3a. We predict that the effects of the CAA intervention on alcohol consumption and consequences will be mediated by increases in (a) positive attitudes towards moderate drinking and (b) dissonance (but not perceived norms). Aim 3b. We predict that the effects of the PNF intervention on alcohol

consumption and consequences will be mediated by decreases in (a) perceived descriptive norms and (b) dissonance (but not attitude change).

Aim 4. Test intervention-specific moderators of outcome. Aim 4a. We predict that the effect of the CAA intervention will be enhanced by stronger drinker identity, greater need for consistency, and will not differ by study site. Aim 4b. We predict that response to the PNF condition will be enhanced by weaker drinker identity, greater need for consistency, and will be stronger within a lighter drinking community (the Houston site).

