6. STUDY POPULATION

6.1. Target Sample. The target sample for analyses is $N=600$ college student drinkers: 300 from Brown University, and 300 from the University of Houston. We will randomize 100 eligible students from each site to the CAA ($n=200$), PNF ($n=200$), and AO ($n=200$) conditions.

6.2. Inclusion Criteria. Inclusion criteria are:

(1) **Age 18-26.** The age range of 18-26 (a) coincides with the distinct developmental period of “emerging adulthood” (Arnett, 2005), (b) is characterized by a high prevalence of heavy episodic drinking (Johnson et al., 2012), and (c) is representative of college students, the majority of whom are 26 years of age or younger (Digest of Education Statistics: 2012).

(2) Male or female student at Brown University or University of Houston. The present study represents a first step in using counter-attitudinal advocacy activities in an attempt to reduce risky drinking behavior. As such, we focus on college students because they exhibit high rates of heavy episodic drinking (Johnson et al., 2012), and their identification with other college peers facilitates the testing of the enhanced manipulation. We recruit at 2 sites that differ in drinking patterns and demographics and geographic location to evaluate the generalizability of the study findings. The findings could have implications for alcohol abuse prevention both with college students and young adults more broadly.

(3) Past month heavy episodic drinking (for men, ≥ 5 drinks in one day, for women ≥ 4 drinks in one day). The 4/5 drink cutoff has been widely used as an indicator of risk ([name], Larimer, & Lewis, 2004; Wechsler & Nelson, 2001) and as a screening criterion in intervention studies targeting heavy drinking students. Our preliminary studies show that heavy drinking frequency is significantly correlated with attitudes towards moderate ($r = -.42$) and heavy ($r = .45$) drinking. By including only drinkers who have reported heavy episodic drinking we optimize the likelihood that developing arguments in favor of moderate drinking ($<4/5$ drinks/occasion) will constitute counter-attitudinal advocacy, and create dissonance between the espoused attitude in favor of moderation and recent behavior.

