13. Provide the analysis plan including the power calculation(s). There should be discussion of any planned interim and/or futility analyses, including adjustments for allocating “alpha” on “multiple looks” at the data.

Sample size and power calculations. Power analyses focus on estimating a sample size large enough to detect “true” effects, thereby avoiding Type II errors. Sample size estimates were obtained for intervention contrasts. Necessary sample sizes were assessed via sample size and power equations for multi-level models using the Optimal Design software program.

Based on previous findings using CAA and PNF approaches, we anticipate intervention effects relative to the neutral control condition to be in the small to medium range but at least comparable to effects which have been reported for personalized normative feedback, which are typically in the .28 range (e.g., Dotson et al., 2015). Based on the proposed sample size of 600, given four assessment points, we anticipate the ability to detect effects of intervention contrasts and moderation effects across the small to medium range.

Considering maximum anticipated attrition rates of 15% (N=510) we will have .70, .80, and .90 power to detect effects sizes of delta = .24, .27, and .32, respectively.

14. Provide the study stopping rules part of the study protocol. Generally, stopping rules reflect one of the following conditions: 1) there is clear evidence of harm; 2) there is no likelihood of demonstrating treatment benefit (futility); 3) there is overwhelming evidence of the benefit of treatment.

There are no study stopping rules associated with the current protocol. Based on prior research, there is no reason to believe that the interventions used in this study could cause harm. Therefore, we do not plan interim analyses prior to achieving our full sample. We anticipate that the full sample will be needed to have sufficient power to detect significant group differences.

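### The .28 planning effect in section 10.1 matches PNF's effect on drinking quantity only; at the .157 that 10.2 quotes for consequences, the plan's own power curve gives about 36% to 42% before any multiplicity correction

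*Combined protocol and SAP*

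**What the plan says.** Section 10.1 expects the interventions to differ from control by amounts "at least comparable to effects which have been reported for personalized normative feedback, which are typically in the .28 range", and cites the 2015 meta-analysis of stand-alone PNF. On that basis it says N = 600 can detect intervention contrasts and moderation effects throughout the small-to-medium band. It then gives the power figures: "Considering maximum anticipated attrition rates of 15% (N=510) we will have .70, .80, and .90 power to detect effects sizes of" .24, .27 and .32. Item 13 of the DSMP (Appendix E) repeats this, including "which are typically in the .28 range".

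Section 10.2, when deriving the Aim 2 margins, quotes two estimates from the same meta-analysis: "drinking quantity ($d = .289$, 95% CI [0.117, 0.451"] and "consequences ($d = .157$, 95% CI[0.037, 0.278"].

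Aim 1 (section 4) is the primary hypothesis, CAA against assessment-only control. It predicts that CAA will "decrease drinks per drinking day, binge frequency, peak BAC, and alcohol consequences, and increase the use of PBS". Section 10.2 lists eight Aim 1 outcomes, consequences among them, and applies a Bonferroni/Šídák correction across them.

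Neither 10.1 nor DSMP item 13 states the alpha, the sidedness or the variance inputs behind the power figures. Neither gives a power for any effect below .24.

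**The concern.** The .28 in section 10.1 is presented as the typical PNF effect. By the plan's own quotation it is the effect on drinking quantity; the effect on consequences is a little over half as large (.157/.289 = .54). Consequences are named in the primary hypothesis, and the CAA task is built around avoiding them. A reader of 10.1 would take the power statement to cover all Aim 1 outcomes about equally, and could then read a null result on consequences as coming from an adequately powered test. If CAA works as well on consequences as PNF is quoted to do, the planned test would miss significance more often than not.

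**Working it through.** **Inputs.** Three arms of 200 (section 6.1). 15% attrition: 600 × .85 = 510, or 170 per arm. Stated powers .70/.80/.90 at δ = .24/.27/.32 (10.1). PNF against control: .289 for quantity, .157 for consequences (10.2). Eight outcomes in the Aim 1 correction (10.2). Assumptions: alpha .05, with sidedness shown both ways, and the plan's δ on the same standardized scale as the meta-analytic d, as 10.1 implies by comparing them.

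**Step 1: reproduce the stated powers.** Formula: power = Φ(d/SE − z), ignoring the negligible opposite tail.

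*Two-sided .05.* Solve SE = δ/(1.960 + z_power):
- .24/(1.960 + .524) = .0966
- .27/(1.960 + .842) = .0964
- .32/(1.960 + 1.282) = .0987

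Allowing each δ ±.005 for rounding, the SEs that fit all three run from .0972 to .0982. This corresponds to an effective 207 to 212 per arm (2/SE²), which is a plausible gain from repeated measures over 170.

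*One-sided .05, simple comparison of 170 per arm.* SE = √(2/170) = .1085, giving .715, .801 and .904. This also reproduces all three.

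A simple two-sided comparison of 170 per arm gives .60, .70 and .84 and does not fit. The stated figures are therefore coherent, but they do not reveal which test was used.

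**Step 2: extend the same curve, without multiplicity correction.**

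| d | Two-sided .05, SE .0972 to .0982 | One-sided .05, 170 per arm |
|---|---|---|
| .289 (quantity) | .84 | .85 |
| .28 (planning value) | .81 to .82 | .83 |
| .20 | .53 to .54 | .58 |
| .157 (consequences) | .36 to .37 | .42 |

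Example, two-sided: .157/.0982 = 1.599, and Φ(1.599 − 1.960) = Φ(−.361) = .36. One-sided: .157/.1085 = 1.447, and Φ(1.447 − 1.645) = Φ(−.197) = .42.

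The row at .20 takes the conventional value for a small effect, since the plan does not define the term.

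**Step 3: add the planned correction.** Šídák alpha for eight independent tests: 1 − .95^(1/8) = .0064, two-sided z = 2.727. With SE .0972 to .0982:
- d = .157: about .13
- d = .289: about .59 (.586 to .597)
- d for 80% power: (2.727 + .842) × SE = .347 to .350, about .35

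The plan intends to adjust for correlation among outcomes but gives no correlations. The corrected power at .157 therefore lies between about .13 (independent outcomes) and .36 (no correction).

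**Step 4: scale of the gap.** Scaling from the stated 80% at .27, 80% power at .157 without correction would need 170 × (.27/.157)² ≈ 503 completers per arm, about three times the 170 expected. This shows size only; it is not a proposal to enlarge the trial.

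**The case against.** *No arithmetic is wrong.* This stands. A reader might infer that the powers in 10.1 are miscalculated. They are not shown to be: all three reproduce. The fault is that the planning effect fits one outcome and is written as if it fitted all.

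*The 36% depends on an unstated test.* This also stands, which is why 36% and 42% must be given together. The conclusion survives either choice: both are below one half.

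*.157 is a PNF figure, not a stated CAA effect.* Section 10.1 draws on both CAA and PNF findings and expects effects at least as large as PNF's. The CAA task addresses consequences directly, and the upper confidence limit for PNF is .278. A larger CAA effect is possible. But 10.1 chose PNF as its benchmark and used the quantity point estimate; the matching value for consequences is .157. The power figure is conditional on that benchmark and should be worded so.

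*The documents already show both numbers.* They print .157 in the section after the power statement, and no sentence claims adequate power for consequences specifically. But the small-to-medium claim is general, and it fails at .20 as well.

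*Two extensions that do not hold.* Consequences are also an Aim 2 outcome, so a reader might carry the 36% over to Aim 2. That test compares CAA with PNF against its own margins (.0585 and .0185), and power for a difference from control says nothing about it. A reader might also conclude that any non-significant result on consequences is inconclusive. With SE about .098 the 95% half-width is about .19; an estimate of −.05 would have an upper limit of about .14, which excludes .157.

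**Conclusion.** The point holds for Aim 1. The sample-size justification rests on an effect that its source, as quoted in the plan, supports for quantity but not for consequences. At the benchmark PNF effect on consequences, power is about 36% (two-sided .05) or 42% (one-sided .05), before correction. With the eight-outcome correction it falls to as low as about 13%; even quantity drops from about 84% to about 59% if outcomes are independent, and less far if they are correlated. The claim to detect intervention contrasts throughout the small-to-medium band is not supported, since power at .20 is 53% to 58% uncorrected.

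These figures rest on alpha .05, on an SE inferred from the stated powers (two-sided) or from 170 per arm (one-sided), and on a common effect-size scale. The mismatch between .28 and .157 needs none of these assumptions; it is in the text. The documents give no figures with which to check the moderation part of the same claim, so nothing is concluded about it.

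**What to change.** In section 10.1 and DSMP item 13:

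1. State the alpha and sidedness used for the power calculation.
2. Replace the single planning value with outcome-specific inputs: .289 for quantity and .157 for consequences.
3. For each, give power both without correction and under the planned multiplicity correction, with the correlation assumed.
4. For intervention contrasts, replace the small-to-medium claim with the smallest effect detectable at 80% power: about .27 uncorrected, about .35 at the independent-test Šídák alpha.
5. State that the consequences contrast has low power at the benchmark PNF effect and will be reported with its confidence interval, so that the interval rather than the p-value shows which effects remain plausible.

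The cost is restated figures in two places and a less favourable power statement. No extra participants and no change of design are needed.
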